12) To answer the secondary research questions, starting in the second month after implementation, study manager will carry out **in-depth interviews** (or small focus group discussions) with providers at sites in both study groups. We will interview providers who use the paper partograph or the ePartogram to discuss barriers and facilitators to usage, including facility conditions. The supervision for providers around the ePartogram and paper-partograph use will also be explored. The interviews will be audio-recorded to capture all contributions from participants. Participants will be informed about this during consenting. The digital recorders erased/audio tapes will be destroyed after transcription and the recordings will not be used for any other purposes.

B. Provide a **sample size and a justification** as to how you arrived at that number. If you use screening procedures to arrive at a final sample a table may be helpful.

The third study objective deals with clinical actions for complications and requires the largest sample size due to the rarity of complications. We describe inputs to sample size as shown in Table 1.

Inputs to the sample size calculation are as follows:

- *Number of sites*: The available 12 sites (6 in each study arm) have 1342 births per month, , on average. So 6 facilities have 671 births per month. We believe 80% of these will have a partograph completed during the study.
- *Prevalence*: Kenya QoC report⁹ stated that “19% of labors crossed the partograph ‘action line’”. While this appears high, we also will look for labors with more than one abnormal measurement signaling an early complication. (A study by Orji et al in Nigeria in 2008 also found 18.5% of labors crossed the action line.) For our study, we use the 19% to indicate that up to 19% of labor may cross the action line OR may have 1+ abnormal measurement that signal need for provider action.
- *Average cluster size*: is calculated to be 17.6
- *Intraclass correlation*: ICC is expected to be high as the facilities are a heterogeneous mix of district hospitals, health centers and some private facilities, so we assume ICC of 0.15.
- *Coefficient of variation*: COV is assumed to be 90%, after calculating the standard deviation of the average monthly births in these sites. Therefore, the design effect is high at 5.3, calculated as follows: $1 + ((\text{average cluster size } 16.4 - 1) * (1 + (\text{COV } 0.80^2)) * \text{ICC } 0.15)$.

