- *Outcome indicator*: The value for the outcome, ‘appropriate clinical actions for complications’, is unknown and thus 50% gives the most conservative estimate for the facilities in the control group using the paper partographs.
- *Effect size*: We expect a 30% point improvement on this indicator in facilities using ePartogram, the intervention sites, to 80%.

Adjusted for design effect, the total number of partographs or ePartograms needed are 1004 per study group, or 2009 in both groups. Due to the fact that there may be additional changes to facility selection, this number of partographs to review may increase somewhat based on the formulas. So we request the number of partographs to review to be up to **2,200 in total** .

Table 1. Sample Size Calculation Parameters

Table 1. Sample size scenarios for ePartogram effectiveness study

Availability of partographs in selected sites per month	536.8	Proportion of all births that have a partograph filled out	80%	671	1342	All 12 facilities - births monthly
Cluster size (Average) (formula based on 3 cells)	17.0					
Intra-class correlation coefficient (ICC)	0.15					
Number of clusters (facilities) PER ARM	6	(total 12 facilities in both study arms)				
Proportion of women whose labor crosses the Action line (a)	19%		Design effect (formula based on cells)	5.3		
Coefficient of variation (determined from number)	90%					
Effective Size: Detecting difference between arms on main indicator: "Case is appropriately managed"	Comparison group	ePartogram group	Unadjusted sample size (in a simple random sample) to detect difference	Adjusted for design effect	Total no of partographs required per arm	Total no of partographs or ePartograms: both study arms
	50%	70%	90	482	2536	5071
	50%	75%	55	293	1543	3087
	50%	80%	36	191	1004	2009

Sample size for qualitative interviewing

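### The design-effect expression printed in Section III.B gives 4.79, not 5.3, and disagrees with Table 1; its form also understates the design effect by 0.12

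*Combined protocol and SAP*

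**What the plan says.** Section III.B lists the inputs to the sample size and refers to Table 1 for them.

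- **Average cluster size.** The bullet says it "is calculated to be 17.6". The worked expression two bullets later uses 16.4. Table 1, in the row "Cluster size (Average) (formula based on 3 cells"), shows 17.0.
- **COV.** The bullet says "COV is assumed to be 90%, after calculating the standard deviation of the average monthly births in these sites", and Table 1 also shows 90%. The worked expression in the same bullet uses 0.80.
- **ICC.** 0.15 throughout.
- **Design effect.** "Therefore, the design effect is high at 5.3, calculated as follows", followed by an expression of the form 1 + (m − 1) × (1 + COV²) × ICC. Table 1 also shows 5.3.
- **Result.** For 50% v 80%, Table 1 runs from 36 unadjusted, to 191 after the design effect, to 1004 partographs per arm and 2009 in both arms. The plan asks to review up to 2,200, to allow for changes in facility selection.

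The section gives neither a significance level nor a power.

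**The concern.** The design effect multiplies every row of Table 1, so the stated sample size depends on it. Here the calculation shown does not produce the number it is offered to support, and a reader meets three cluster sizes and two COVs with nothing to say which are current. The COV matters most, because it is said to have been calculated from the births at these sites, yet two values are printed in one bullet.

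The practical risk is in reuse. The section expects that the number may have to be reworked if the facilities change. Anyone who reworks it from the printed line would start from a target about 10% below the plan's own. The form of the expression is a second, independent matter: it takes 1 from the mean cluster size before inflating for unequal sizes, and so understates the design effect.

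**Working it through.** **Inputs.** Section III.B states: "So 6 facilities have 671 births per month"; "We believe 80% of these will have a partograph completed during the study"; and "we use the 19% to indicate that up to 19% of labor may cross the action line". ICC is 0.15, there are 6 facilities per arm, and the proportions are 50% and 80%. Two-sided alpha 0.05 and 80% power are my assumption, with z = 1.96 + 0.84 = 2.80.

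**1. Reproduce Table 1.**

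- Partographs per arm per month: 671 × 0.80 = 536.8.
- Mean cluster size: m = 536.8 × 0.19 / 6 = 17.0 (16.9987).
- Design effect in the plan's form: 1 + (16.9987 − 1) × (1 + 0.90²) × 0.15 = 1 + 15.9987 × 1.81 × 0.15 = 5.34, shown as 5.3.
- Unadjusted size, unpooled variance: n₀ = 2.80² × (0.25 + p₂(1 − p₂)) / (p₂ − 0.50)².
- Partographs per arm: n₀ × DE / 0.19.

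| p₂ | n₀ | × DE | Per arm | Both arms | Table 1 |
|---|---|---|---|---|---|
| 70% | 90.16 | 481.8 | 2,535.7 | 5,071.4 | 90; 482; 2536; 5071 |
| 75% | 54.88 | 293.3 | 1,543.5 | 3,086.9 | 55; 293; 1543; 3087 |
| 80% | 35.72 | 190.9 | 1,004.5 | 2,009.0 | 36; 191; 1004; 2009 |

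All three rows match. A pooled-variance formula gives 39 in place of 36 for the last row, so it is not the one used.

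**2. Evaluate the text's inputs in the same form, for 50% v 80%.**

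| Source | m | COV | Design effect | Per arm | Both arms |
|---|---|---|---|---|---|
| Printed expression | 16.4 | 0.80 | 1 + 15.4 × 1.64 × 0.15 = 4.79 | 900 | 1,800 |
| Bullets | 17.6 | 0.90 | 1 + 16.6 × 1.81 × 0.15 = 5.51 | 1,035 | 2,070 |
| Table 1 | 17.0 | 0.90 | 5.34 | 1,004.5 | 2,009 |

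The printed expression falls about 10% below 1004 and the bullets about 3% above it. Only Table 1's inputs return it.

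**3. Check the form of the expression.** With unequal clusters, the quantity that replaces m is Σmᵢ²/Σmᵢ = m(1 + COV²). The design effect is therefore 1 + ((1 + COV²)m − 1) × ICC. A small case shows the difference. For clusters of 1 and 3, m = 2, COV² = 0.25 and Σmᵢ²/Σmᵢ = 10/4 = 2.5. The design effect is then 1 + 1.5 × ICC, whereas the printed form gives 1 + 1.25 × ICC. The shortfall is always COV² × ICC, here 0.81 × 0.15 = 0.12.

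**4. Apply the corrected form to Table 1's inputs.**

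- DE = 1 + (1.81 × 16.9987 − 1) × 0.15 = 5.47 (5.465).
- Per arm: 35.72 × 5.465 / 0.19 = 1,027.
- Both arms: 2,055.
- Against the plan: 1,027 / 1,004.5 = 1.023, or 23 more per arm.

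**5. If 0.80 is the true COV, with m = 17.0.** DE = 1 + (1.64 × 16.9987 − 1) × 0.15 = 5.03. Per arm, 35.72 × 5.03 / 0.19 ≈ 946.

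**The case against.** The strongest reply is that the section sends the reader to Table 1 for its inputs, and that Table 1 is internally correct. Both the COV bullet and the table say 90%, and only 17.0 with 90% returns the table's figures, so there is little doubt about what was computed. On this view the text carries a few wrong numbers beside a right result, possibly left from another site list, though the documents do not say so. The formula term is worth about 2%, which is small beside the uncertainty in an assumed ICC of 0.15, and every variant above stays under 2,200.

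Most of this stands. A reader might infer that 5.3 and 1004 are miscalculated or unsupported, or that the required size is unsettled anywhere between the lowest and highest figures that the printed inputs allow. The documents do not support either reading: 1004 was not computed from 16.4 and 0.80, and all of Table 1 can be rebuilt from its own inputs.

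The reply does not remove the error in the text. An expression offered as the calculation of 5.3 evaluates to 4.79, and the bullet that justifies the COV contains two values for it. Nor does the small size of the formula term make the form right.

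**Conclusion.** The point holds, and its size is modest. The worked expression and the cluster-size bullet in Section III.B are wrong as written and conflict with Table 1, whose arithmetic is sound under the plan's formula. That formula understates the design effect by 0.12. Correcting it on Table 1's inputs moves the design effect from 5.34 to about 5.47, and the need from 1004 to about 1,027 per group (2,055 in total).

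This rests on two-sided alpha 0.05 and 80% power, inferred from the match to all three rows of Table 1, and on 0.90 being the intended COV. Carrying z to more decimals (1.96 + 0.8416) moves the per-group figure by only about one record.

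The restated figure should not be taken as a full validation of the sample size. The 17.0 is one month of complicated cases per facility, whereas 1004 per group implies 1004 × 0.19 / 6 = 31.8 per facility. Which period m should cover is a separate question that this point does not settle.

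**What to change.** In Section III.B:

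1. Use one cluster size and one COV in the bullets, the worked expression and Table 1. These are 17.0 and 0.90 if Table 1 is the intended source. If 0.80 is what the site data give, restate Table 1 and everything that follows from it.
2. Print the formula as 1 + ((1 + COV²) × m − 1) × ICC.
3. State the alpha, its sidedness, the power and the variance form used.
4. On Table 1's inputs, restate the design effect as about 5.47 and the need as about 1,027 per group (2,055 in total), and carry the change through the other two rows.

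The cost is protocol wording. The restated total is 46 above 2009 and leaves 145 of the 191 records that separate 2009 from 2,200, so this correction alone needs no larger request.

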Routine use of paper partograph in low- and middle-income countries is low and inconsistent.^{7,88} In many settings, partographs are completed retrospectively for record-keeping purposes only. The MCHIP Quality of Care Study in Kenya in 2010⁹ found that “the partograph was widely used during labor (in 88% of 442 cases), and when used, its use was initiated at the correct time in more than 90% of the cases. Providers were less consistent in filling in details on the partograph during labor and delivery, with all components completed in only 58% of cases.” In cases where the partograph action line was reached (in 19% or 78 cases), the appropriate action was taken 78% of the time.

Innovation

The **ePartogram**, developed by Jhpiego and partners, is an Android tablet-based application based on the modified WHO paper-based partograph for use by SBAs to monitor labor. As when using the paper partograph in labor and delivery settings, SBAs using the ePartogram obtain clinical measurements from the woman and fetus according to the current standard of care. The measurements are entered into the ePartogram, which will then plot the data in the familiar modified WHO partograph format (see Appendix A and Appendix B). The ePartogram is designed to increase timely utilization of the partograph (and thus improve labor management outcomes) by addressing key challenges in paper partograph use and interpretation. These challenges include data entry not being straight-forward, and lack of real-time data collection, detection of complications, and awareness on when to take clinical action. The ePartogram electronically captures data and triggers warnings to reinforce clinical expertise and action by providers; it never touches the woman and will only be used by SBAs for recording measurements and interpretation.

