 - a) In both study arms, providers will receive training on labor management and partograph usage per national and international WHO guidelines. Providers will be encouraged to consult their supervisor available when complications arise during labor, as per the standard-of-care. In the ePartogram study group only, a two-day training on ePartogram tablet use and maintenance will be given.
 - b) All providers in both study arms will be consented prior to the training.
 - c) ePartogram facilities will have the data transmitted over a cloud database accessible only to study staff.
 - d) An onsite facility staff will cover client identifiers and scan partographs and photograph registers for sending to a secure cloud folder. Client identifiers will be covered up prior to transmitting information.
 - e) Jhpiego study clinicians will access the scanned partographs and registers or ePartogram database online, and abstract the relevant data into the Partograph Extraction Tool 4 Revised and also the Register Review Tool 6. This data will be analyzed further by Jhpiego data analysts.
 - f) A study coordinator will be on call for any technical or software issues with the ePartogram, and backup tablets will be stored on site.
 - g) Note: if any clients in the ePartogram facility group are followed with a paper partograph, we will capture this info and consider this data to belong to the ePartogram group. We believe these providers would have been influenced by the use of the ePartogram in the facility.
 - h) Starting in second month, the study staff will collect qualitative interviews with SBAs, audio record, and transcribe for further analysis

Table 3

Study Timeline	Mar	Apr	May	June	July	Aug	Sept	Oct	Nov
Activity									
Ethical review by JHSPH and KEMRI	X	X	X						
Finalize training materials		X	X						
Facility and stakeholder orientation visits		X	X						
Facility stockup on supplies		X	X						
Data collector training		X	X						
Provider trainings			X	X					
Data collection			X	X	X				
Partograph Review and Data analysis			X	X	X	X	X		
Dissemination Meeting								X	

Table 4. Tools

The following are data collection or abstraction tools to be used in this study.

Tool No.	Tool Name	Description

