At the start of the study, the study trainers will offer a training workshop in each study group. Thereafter, the study coordinator will visit each site monthly to collect ePartogram case information. Local staff who work in records management or the nurse in-charge will be asked to scan partographs daily and registers weekly and send the data on the study-loaned laptop to a secure cloud database. Direct interaction with study team members may occur only once per month since we will mainly collect data on paper. If a provider is having trouble with the ePartogram, then more than one interaction with study staff is possible.

A subset of providers will be asked to participate once in an in-depth interview lasting 45 minutes. These providers will have 2 contacts.

3. Describe the expected **duration** of the study from the perspective of the individual participant and duration overall.

The number of months of the use of the ePartogram at intervention sites and data collection (capture of labor information on clients) at sites in both study arms will take **up to 9 months**. We expect to collect all partograph information over 2 or 3 months, depending on volume of births and the percent covered by partographs during the actual period of study implementation.

4. Provide a **brief data analysis plan and a description of variables to be derived.**

We will compare study groups (facilities in which providers are using the ePartogram and facilities in which providers are using the paper partograph):

Table 5: Data Analysis Plan (updated July 2016; updated July 2017)

Research question	Outcome	Cases	Analysis

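### P3 sample size: 50% is not the most conservative control value, the 78% in the Background is not addressed, and the design effect rests on one month's cases per facility

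*Combined protocol and SAP*

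**What the plan says.** Section III.B sizes the study on P3, appropriate action for complications. It says the control value "is unknown and thus 50% gives the most conservative estimate for the facilities in the control group using the paper partographs". On the effect it says "We expect a 30% point improvement on this indicator in facilities using ePartogram, the intervention sites, to 80" per cent. All three scenarios in Table 1 keep the control value at 50% and vary only the gain (20, 25 or 30 points). The 50% versus 80% row gives 36 cases per arm unadjusted, 191 after the design effect, 1,004 partographs per arm and 2,009 in total. Up to 2,200 are requested.

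The prevalence comes from the Kenya quality-of-care report: "For our study, we use the 19% to indicate that up to 19% of labor may cross the action line". The Background (Section II) cites another result of that report: "In cases where the partograph action line was reached (in 19% or 78 cases), the appropriate action was taken 78% of the time". The sample-size text does not mention it.

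The design effect of 5.3 uses an average cluster size of 17.0. Table 1 derives this from a monthly count, labelled "Availability of partographs in selected sites per month" (536.8 for six facilities). On duration, Section V.C.3 says "We expect to collect all partograph information over 2 or 3 months, depending on volume of births".

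**The concern.** A value of 50% maximises the variance of one proportion. It does not maximise the sample size for a difference between two proportions, which depends on both values and on the gain. Calling it most conservative tells the reader that any other control value would be easier to study, and that is not so.

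The report that supplies the 19% also contains a figure for appropriate action, and it lies well above 50%. If control performance in P3 were high, little room would be left for improvement. A null result could then mean either no benefit or no room to show one. P3 drives the study size, and Section I says the result will inform the Ministry of Health on wider use.

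The cluster size is a separate matter. It comes in here because any added row for another control value would inherit the design effect.

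**Working it through.** **Inputs.** From Section III.B and Table 1: control 50%, target 80%, prevalence 0.19, six facilities per arm, ICC 0.15, CV 0.90, 536.8 partographs per month per arm, 1,004 per arm needed, 2,200 in total requested. Alpha and power are not stated. I assume two-sided 5% and 80%, because these reproduce Table 1.

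**1. Reproducing Table 1.** n = (1.96 + 0.8416)² × (p1q1 + p2q2) / (p2 − p1)², where q = 1 − p and (2.8016)² = 7.849.
- 50/70: 90.3; 50/75: 54.9; 50/80: 7.849 × 0.41 / 0.09 = 35.8. Table 1 has 90, 55 and 36.
- Cluster size: 536.8 × 0.19 / 6 = 17.0.
- Design effect: 1 + (17.0 − 1) × (1 + 0.90²) × 0.15 = 5.34. (The formula printed in the text uses 16.4 and 0.80, which gives 4.79. The Table 1 inputs are the ones that match 5.3.)
- 35.8 × 5.34 / 0.19 is about 1,006 per arm, against 1,004 printed, which is rounding.

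**2. Other control values, before clustering.**

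| Reading | Control/target | n per arm |
|---|---|---|
| 30-point gain | 20/50 | 35.8 |
| | 35/65 | 39.7 |
| | 50/80 | 35.8 |
| | 60/90 | 28.8 |
| | 65/95 | 24.0 |
| 80% target | 60/80 | 78.5 |
| | 65/80 | 135.2 |

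For a 30-point gain the peak is at 35/65: 39.68 / 35.76 = 1.11, and 2,009 × 1.11 is about 2,230 partographs, just above the 2,200 requested. Every control value strictly between 20% and 50% needs more than 50% does. From 50% to 70% fewer cases are needed. For an 80% target, scaling 1,004 by 78.5/35.8 and 135.2/35.8 gives about 2,200 and 3,800 partographs per arm.

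**3. Headroom.** At a control value of 78% the largest possible gain is 100 − 78 = 22 points. Any value above 70% rules out a 30-point gain.

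**4. Cluster size.** The 17.0 is one month of cases. At 80% of 1,342 births a month, 2,200 partographs take 2200 / 1073.6 = 2.05 months.

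| | 1,004 per arm | 1,100 per arm |
|---|---|---|
| Cases per arm (× 0.19) | 190.8 | 209 |
| Cases per facility (/ 6) | 31.8 | 34.8 |
| Design effect, plan's formula | 9.36 | 10.19 |
| Effective n, plan's formula | 20.4 | 20.5 |
| Effective n, exchangeable GEE | 30.4 | 31.0 |

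The plan's formula gives every case equal weight. For GEE with an exchangeable working correlation I used the usual approximation for unequal clusters. Effective n = cases / [1 + (m − 1) × 0.15] × [1 − 0.90² × L(1 − L)], with L = 0.15m / (0.15m + 0.85) and m the cases per facility. At m = 34.8, L = 0.860 and effective n = 209 / 6.075 × 0.9025 = 31.0.

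**5. Power and detectable values.** Power = Φ{(p2 − p1) / √[(p1q1 + p2q2) / effective n] − 1.96}.
- 50/80, equal weight: 0.30 / √(0.41/20.4) − 1.96 = 0.16, so power is 56%.
- 50/80, exchangeable GEE: 73% at 1,004 per arm and 74% at 1,100.

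Smallest intervention value with 80% power at 2,200 partographs:

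| Control | Design effect 5.3 as printed | Equal weight | Exchangeable GEE |
|---|---|---|---|
| 35% | 65% | 75% | 68% |
| 50% | 79% | 87% | 82% |
| 65% | 90% | 97% | 92–93% |
| 78% | 98% | not reachable (67% power at 100%) | 99% |

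The normal approximation is rough near 100%. No small-sample correction for 12 facilities is applied, and one would lower power in both of the last two columns.

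**The case against.** The P3 control value may fairly be called unknown. A reader might infer that it is 78% and that the planned gain is therefore impossible. The documents do not support that. The 78% covers action-line cases only, whereas P3 (Section V.C.4, Table 5) covers any complication and is scored by clinical rules applied to extracted records. Incomplete recording could pull the P3 value down: the same report describes partographs "with all components completed in only 58% of cases". Training could push it up: "In both study arms, providers will receive training on labor management and partograph usage per national and international WHO guidelines". What stands against the plan is that it neither cites the figure nor says why it does not carry over.

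It can also be said that the error over 50% is small, at most 11% for a 30-point gain, and that above 50% a fixed gain needs fewer cases. Both are true. It would be wrong to read the point as every higher control value needing more cases. The difficulty with a high control value is the smaller gain available. Table 1 does show smaller gains, but never a different control value.

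The loss of power at 50/80 comes from the cluster size and has nothing to do with the 78%. That is correct, and the two issues should be kept apart.

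A reader might also infer that six facilities per arm cap effective n at 6 / (1.81 × 0.15) = 22.1, and power for 50/80 at about 60%, however many partographs are read. That holds only with equal weights. Section V.C.4 plans GEE without naming a working correlation, and under an exchangeable one the ceiling is 6 / 0.15 = 40. Power must therefore be given as a range.

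Lastly, the pairing of 78 cases with 78% might look like a copying slip. The protocol does not give the denominator for the 19%, so nothing follows.

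**Conclusion.** The claim that 50% is most conservative is wrong under either reading of the stated effect: by up to 11% for a 30-point gain, and by a factor of 2.2 (78.5/35.8) or more for an 80% target once the control value reaches 60%. The only earlier figure for appropriate action in the protocol is left unaddressed, so the headroom for a gain is not shown. It is not evidence that P3 control performance is 78%.

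Separately, the printed design effect does not fit the planned size. On the plan's own ICC and CV, 2,009 to 2,200 partographs give about 56% (equal weight) to 74% (exchangeable GEE) power for 50% versus 80%. The protocol states no power, so this contradicts the 80% implied by Table 1 and not a written claim. The arithmetic on control values and the design effect is firm. The power range depends on the assumed alpha, ICC and CV and on the unstated working correlation.

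**What to change.** 1. In Section III.B, describe 50% as an assumption and remove the statement that it is most conservative.
2. Cite the 78% there and say how far it applies to P3: action-line cases only, with different scoring.
3. Add Table 1 rows for other control values, for example 35%, 65% and 78%, giving the smallest intervention value detectable at 2,200 partographs. Use the cluster size the study will have (about 32 to 35 cases per facility). Show the equal-weight and exchangeable-GEE results as a range, marked as approximate and before any small-sample correction.
4. State the alpha and power assumed (two-sided 5% and 80% reproduce Table 1). Restate that 2,009 to 2,200 partographs give about 56% to 74% power for 50% versus 80%.

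The cost is wording, a few table rows and a less favourable stated figure. No extra partographs are asked for.
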